9.2.4.2. Disease Characteristics and Previous AD Treatments

At the baseline Visit (Visit 1) the presence of a family history of atopic diseases as well as a patient's clinical history regarding herpes simplex, herpes zoster, eczema herpeticum will be documented. Furthermore, the age at initial diagnosis of AD, previous treatments for diagnosed AD as well as current comorbidities of interest (atopic diseases: asthma, allergic rhinitis, food allergies, nasal polyps; malignancies, cardiovascular diseases) and concomitant non-AD specific treatments will be documented. At the baseline visit the number of flares as well as the number of hospitalizations and the number of absent days at work/study caused by AD during the last 12 months prior to start of abrocitinib will be documented. At each of the subsequent visits (Visit 2-6), the number of flares, the number of hospitalizations due to AD, as well as the number of absent days at work/study since the last documented visit will be captured.

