9.2.4.6. Concomitant Treatment for Atopic Dermatitis

At each visit (Visit 1-6) dose and type of concomitant treatment will be documented. At baseline visit the number of days with topical-treatment use (TCS, TCI) and emollients use three months before start of treatment with abrocitinib (first visit) and at each subsequent visit number of days with topical- treatment use (TCS, TCI) and emollients use days since the last visit (follow-up visits) will be assessed.

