EASI	X	X	X	X	X	X

Study period based on routine visits	Baseline (Enroll ment)	Month 1	Month 3	Month 6	Month 9	Month 12 End of Study (EoS)
IGA	X	X	X	X	X	X
Pruritus-NRS	X	X	X	X	X	X
PP-NRS	X	X	X	X	X	X
DLQI	X	X	X	X	X	X
POEM	X	X	X	X	X	X
MOS	X	X	X	X	X	X
PBI	X	X	X	X	X	X
EQ-5D-5L	X	X	X	X	X	X
HADS	X	X	X	X	X	X

^{*} This includes patients who discontinued treatment with abrocitinib.

Figure 1. Timelines

The planned observation period of each patient is 12 months. In this time period up to 6 visits will be documented.

Figure 2. Study Period

Table 2. Definition of time windows for study visits

In order to collect comparable study data, Visits 1 to 3 occurring ± 14 days and Visits 4 to 6 occurring ± 28 days of the scheduled visit date will be used for data analysis (interim analysis).

Visit Label	Target Day	Definition [Day window]
Enrolment	1	1
Month 1	30	16 to 44
Month 3	91	77 to 105
Month 6	182	154 to 210
Month 9	273	245 to 301
Month 12	365	337 to 393

Visits that do not meet the defined windows as displayed in the table above will also be included in the final analysis and clinical study report. Therefore, all visits will be included using the visit time slots shown below. If more than one visit appears in a 3-month window, only the visit closest to the target day will be respected.

Amended definition:

Visit designation	Target Day	Definition [Day window]
Enrolment	1	1
Month 1	30	2 to 44
Month 3	91	45 to 105
Month 6	182	106 to 210
Month 9	273	211 to 301
Month 12	365	302 to 393

However, for analysis of safety parameters, all AEs/SAEs documented within the applicable reporting period will be analyzed.

- For the lab values, if the calculated study day for the labelled baseline visit is not study Day 1, but falls within 40 days before the start of the study dosing, then that data should be used for the baseline instead of leaving baseline missing.
- For the other values, if the calculated study day for the labelled baseline visit is not study Day 1, but falls before the start of the study dosing, then that data should be used for the baseline instead of leaving baseline missing.
- If baseline is missing there will be no imputation and although the subject's data will be included in summary data it will not be included in any change from baseline analyses.

If two or more routine visits fall into the same window, keep the one closest to the Target Day. If two routine visits are equal distance from the Target Day in absolute value, the later visit should be used.

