11 APPENDICES

11.1 APPENDIX 1: DATA DERIVATION DETAILS

EASI-75-responder: Percentage of patients with 75% reduction from baseline in EASI EASI-90-responder: Percentage of patients with 90% reduction from baseline in EASI SCORAD-75-responder: Percentage of patients with 75% reduction from baseline Abrocitinib responder: EASI-75-responder and/or SCORAD-75-responder and/or IGA 0/1

Number of days with topical treatment use (TCS, TCI): Date of first topical treatment – date of last topical treatment + 1

Number of days with emollients use: Date of first emollients use – date of last emollients use + 1

 $\underline{Days\ of\ AD\text{-treatment:}}\ Date\ of\ last\ AD\ treatment-date\ first_AD\text{-treatment}+1$

Age [years]: Year of informed consent – year of birth

Age at initial diagnosis of AD [years]: year of initial diagnosis – year of birth

Percentage change to baseline: (score at respective visit – score at baseline)/score at baseline*100

Information of additional documentation timepoints will be added to the information of the next scheduled visit and analyzed at the scheduled visit.

PROs and other questionnaires referring to additional documentation timepoints will not be analyzed but may be of interest if the course of individual patients is considered in more detail.

PROs will be assigned to the month/scheduled visit according to the time windows given below.

A1.1 Definition and use of visit windows in interim analysis

Visit Label	Endpoint	Definition [Day window]
Enrolment	All	1
Month 1	All	2 to 44
Month 3	All	45 to 105
Month 6	All	106 to 210
Month 9	All	211 to 301
Month 12	All	302 to 393

PFIZER CONFIDENTIAL

CT24-WI-GL03-RF02 2.0 Non-Interventional Statistical Analysis Plan For Primary Data Collection Study 01-Jun-2020
Page 38 of 39

A1.2 Further definition of endpoints

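### The one-visit-per-window rule has no exemption for counts recorded since the previous visit, so flares, AD hospitalisations and absent days at a discarded scheduled visit are left in no retained record

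*SAP*

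**What the plan says.** SAP 1.1 gives narrow windows (Months 1 and 3 within 14 days of target, Months 6, 9 and 12 within 28 days) for the interim analysis. For the final analysis it gives amended, contiguous windows: 2–44, 45–105, 106–210, 211–301 and 302–393. Protocol 9.7 has the narrow windows only.

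Both documents reduce each window to one visit: "If two or more routine visits fall into the same window, keep the one closest to the Target Day". For the final analysis the SAP adds: "If more than one visit appears in a 3-month window, only the visit closest to the target day will be respected". The one exemption concerns safety: "for analysis of safety parameters, all AEs/SAEs documented within the applicable reporting period will be analyzed".

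Protocol 9.2.4.2 collects flares, AD hospitalisations and absent days at Visits 2 to 6 as interval counts; for the last of these, "the number of absent days at work/study since the last documented visit will be captured". At baseline each is a single figure for the preceding 12 months. Protocol 9.2.4.6 collects topical and emollient days in the same way: "emollients use days since the last visit (follow-up visits) will be assessed".

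SAP 6.3 analyses flares, hospitalisations and absent days by summary statistics and does not say how counts are combined across visits. Appendix 1 has one carry-forward rule: "Information of additional documentation timepoints will be added to the information of the next scheduled visit and analyzed at the scheduled visit". PROs and questionnaires are excluded from it.

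**The concern.** Keeping the visit nearest the target is reasonable for EASI, IGA or a questionnaire, because the discarded value is a second reading of the same state. An interval count is different. The next visit counts only from the discarded visit onward, so the discarded record is the only one that covers its interval.

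The loss can only lower the follow-up count. The baseline figure is one record and no window trims it. Protocol 9.1.1 f to h set the year before treatment beside the observation period, so a follow-up total built from retained visits would be too low on one side of that comparison. Patients who complete every visit are not protected: the Per Protocol Set in SAP 5.3 requires all visits but disregards their timing. Flares are also compared between subgroups in FAS, mFAS and PP (SAP 8.2.3), and subgroups with less punctual visits would lose more.

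**Working it through.** **Windows.** Targets 91 ± 14 and 182 ± 28 give 77–105 and 154–210, as in the narrow table; the other rows also agree. The amended windows keep the same upper limits and extend each lower limit back to the previous window. A Month 3 visit on day 106, which is 15 days late, therefore falls in the Month 6 window.

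**Worked record.** Scheduled visits on days 30, 108, 185, 275 and 366.

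- Days 108 and 185 both lie in 106–210. Their distances from day 182 are 74 and 3, so day 185 is kept.
- The day-185 record counts events after day 108. The day-30 record counts events up to day 30.
- Uncovered interval: 108 − 30 = 78 days. Follow-up: 366 − 1 = 365 days. Share lost: 78/365 = 21%.
- In the narrow windows day 108 lies between 105 and 154, so it is outside every window and is dropped as well.

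**Size over a cohort.** The documents give no distribution of visit timing, so the following is assumed: five follow-up visits per patient, normally distributed around the target days, 20,000 simulated patients per setting, ties to the later visit. Share lost = sum of (discarded visit day − preceding visit day) over discarded visits, divided by (last visit day − 1), averaged over patients.

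| Assumed scatter | Patients with a same-window discard, amended | Days lost to same-window discards, amended | Days lost including visits after day 393, amended | Days lost, narrow windows, all causes |
|---|---|---|---|---|
| SD 7 | 4% | 0.7% | 0.7% | 1% |
| SD 14 | 31% | 6.5% | 7% | 11% |
| SD 21 | 53% | 14% | 17% | 25% |
| SD 14, 7 days late | 56% | 12% | 14% | 17% |
| SD 21, 7 days late | 69% | 19% | 23% | 31% |

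Two mechanisms must be kept apart. In the amended windows most of the loss comes from two visits sharing a window, and visits after day 393 add at most about 5 points. In the narrow windows same-window discards account for no more than about 0.5% of days; nearly all of the loss there comes from visits outside every window.

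Days lost equal events lost only if events are spread evenly over follow-up.

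**After the change.** If counts from every documented visit are summed, all 365 days of the worked record are covered.

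**The case against.** The strongest reply is that the SAP never says these counts are trimmed. Section 6 refers to Table 2 when describing scale-based endpoints. Scores are summarised at each point in time, whereas flares, hospitalisations and absent days are not. Protocol 9.1.1 words them over the observation period, so whole-period counting is a fair reading. No follow-up sum and no before–after test is defined. In a per-visit table a discarded visit is simply a missing Month 3 value, and the day-185 record remains a valid count for days 108 to 185.

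Much of this stands, and it limits the point to a conditional undercount. It does not remove the gap. The selection rule is written for visits without limit by variable, its only exemption is AEs/SAEs, and the endpoint column of Appendix table A1.1 reads All (although that table is headed as interim). The whole-period wording of the endpoints is itself a reason not to trim the counts.

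A reader might infer that every discarded visit deletes its interval. The documents do not support that. Information from extra visits is carried to the next scheduled visit under Appendix 1. On a plain reading, though, that rule does not reach a scheduled visit that loses its window to another, and a discarded last visit has no later visit to receive its counts.

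A reader might also infer that secondary endpoints j and k lose days in the same way. SAP 6.1 and Appendix 1 derive them from dates: "Date of first topical treatment – date of last topical treatment + 1" and "Date of first emollients use – date of last emollients use + 1". Dropping a middle visit does not shorten such a span. The mismatch between the protocol's counts and the SAP's dates, and the order of subtraction in those formulas, are separate matters.

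**Conclusion.** The point holds for flares, AD hospitalisations and absent days at scheduled visits that are discarded. Followed as written, the selection rule leaves their intervals in no retained record, and any follow-up total from retained visits is undercounted against the 12-month baseline figure. Topical and emollient days join them only if the protocol's since-last-visit counts are what is analysed.

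The size depends wholly on visit timing. Under the assumptions above, same-window discards in the amended windows cost from under 1% to about 19% of follow-up days. With punctual visits (SD 7) the effect is negligible. No visit is mandatory and timing follows clinical practice, so larger scatter is foreseeable but not established.

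It would go too far to say that the plan will report a spurious treatment benefit: the SAP defines neither the follow-up total nor a before–after test. The primary endpoints are point-in-time responses and are not touched by this loss. The change is worth making because the loss can run in one direction only and is cheap to prevent.

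**What to change.** State in SAP 1.1 and Protocol 9.7 that selection by visit window applies to point-in-time assessments only. Flares, AD hospitalisations and absent days, and any other variable analysed as a since-last-visit count, should be taken from every documented visit regardless of window, summed per patient, and related to the days from Day 1 to the last documented visit. This covers same-window discards, visits outside every window and visits after day 393.

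If per-visit tables are also wanted, extend the Appendix 1 carry-forward to any discarded visit, so that its count and its days are added to the next retained visit. A discarded last visit would still enter the per-patient total.

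The cost is a short text change in each document and a small amount of programming, with no new data. Follow-up counts may come out higher, so the apparent reduction from the year before treatment would be smaller.

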
1.2 STUDY POPULATION

In total, this non-interventional study aims to enroll at least 750 patients patients at approximately 80 study sites across Germany. The planned enrollment period is 48 months. With a planned observation duration of 12 months per patient, the entire study would last for 60 months. The non-interventional study started in April 2022 and will end in May 2027.

1.3 STUDY OBJECTIVES

The objectives of this non-interventional study are to examine patient characteristics, usage and effectiveness of abrocitinib in adult patients with moderate to severe AD who have been chosen to start treatment with abrocitinib in a real-world context such as dermatological practices in Germany. The following factors will be considered, if collected as part of the medical routine:

Primary Objective:

The primary objective of this non-interventional study is to describe the efficacy of abrocitinib treatment.

- In terms of patients achieving a clear or almost clear AD morphology 3 months after first prescription of abrocitinib based on the IGA Questionnaire.
- In terms of patients achieving $a \ge 75\%$ improvement in lesion extent and severity 3 months after first prescription of abrocitinib based on the EASI.

Secondary Objectives:

The secondary objectives of this non-interventional study are:

• To document the efficacy of abrocitinib treatment based on physicians'

- assessment:
 Physician's global assessment of AD: Scoring Atopic Dermatitis (SCORAD), EASI, IGA change to baseline.
- To document the efficacy of abrocitinib treatment based on patients' assessment:
 - Patient's global assessment of AD: change in quality of life, Dermatology Life Quality-Index (DLQI), Patient Oriented Eczema Measure (POEM);
 - Patient's assessment of anxiety and depression: Hospital Anxiety and Depression Scale (HADS);
 - Patient's assessment of pruritus: Peak Pruritus Numeric Rating Scale (PP-NRS), mean-NRS and sleep: Medical Outcomes Study Sleep (MOS) Scale;
 - Meeting the patient's expectations (change in the Patient Benefit Index [PBI]) with regard to medical treatment;
 - Number of days with topical-treatment use (topical corticosteroid (TCS), topical calcineurin inhibitor (TCI);
 - Number of days with emollients use.

Explorative objectives:

The explorative objectives of this non-interventional study are:

- *To document patient characteristics and treatment decisions in terms of:*
 - patient characteristics, clinical history, comorbidities and previous therapies;
 - o reasons for starting/ending treatment with abrocitinib, concomitant treatments;
 - o dosage and actual use of abrocitinib as assessed by the treating physician and the patient.
- To assess the safety in terms of adverse and serious adverse events that will occur in the observation period. Severity categories (mild, moderate and severe) of adverse events will be assessed based on investigator's assessment (when applicable).

2 INTERIM ANALYSES

Two interim analyses are planned for this study. Table 3 shows the planned analyses schedule. Results of earlier interim analyses will be updated in each later analysis.

Table 3. Content of Interim analysis

Table 3 Content of Interim Analysis

Analysis	Year	Population cut-off	New Content
Interim analysis 1 (IA1)	Not applicable – see population cut-off	When approximately 15 % of patients completed Visit 1	Baseline characteristics, explorative endpoints as well as usage of abrocitinib and effectiveness at visit 2.
Interim analysis 2 (IA2)	Not applicable – see population cut-off	When approximately 40 % of patients completed Visit 4	Baseline characteristics, explorative endpoints as well as usage of abrocitinib and effectiveness at each available timepoint.
Final analysis	2028	All patients	Patient characteristics, usage and effectiveness, anything not yet analyzed.

Two interim analyses will be carried out. The first interim analysis (IA) will be conducted when approximately 15 % of the planned number of patients have reached their V1 (baseline) visit. The IA1 interim analysis will consider explorative endpoints with focus on baseline characteristics, transition to abrocitinib treatment as well as usage of abrocitinib and effectiveness at visit 2 respectively.

The interim analysis will be repeated (IA2) when approximately 40 % of patients completed visit 4. This interim analysis will consider the same aspects as IA1 and effectiveness at every other available timepoint.

3 FINAL ANALYSES

The final analysis will include all enrolled patients and will be carried out after all patients have reached their final visit (at Month 12). The final datasets will be extracted from the database and locked before final analysis. Any exclusions from the analysis will be agreed and documented prior to database lock.

4 HYPOTHESES AND DECISION RULES

As the protocol states, this is a solely descriptive and explorative non-interventional study with the aim to generate hypothes. In order to generate hypotheses the statistical tests mentioned in section 8.2.3 are carried out for the subgroups defined in section 5.4.

4.1 STATISTICAL HYPOTHESES

Not applicable.

4.2 STATISTICAL DECISION RULES

Not applicable.

5 ANALYSIS SETS/POPULATIONS

5.1 FULL ANALYSIS SET

The Full Analysis Set (FAS) consists of all patients with informed consent who met the eligibility criteria and received at least one dose of abrocitinib. This population will be used for all analyses except safety.

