8. RESEARCH QUESTION AND OBJECTIVES

The objectives of this non-interventional study are to examine patient characteristics, usage and effectiveness of abrocitinib in adult patients with moderate to severe AD who have been chosen to start treatment with abrocitinib in a real-world context such as dermatological practices in Germany. The following factors will be considered, if collected as part of the medical routine:

Research Questions:

Primary Objective:

The primary objective of this non-interventional study is to describe the efficacy of abrocitinib treatment.

- In terms of patients achieving a clear or almost clear AD morphology 3 months after first prescription of abrocitinib based on the IGA Questionnaire.
- In terms of patients achieving a \geq 75% improvement in lesion extent and severity 3 months after first prescription of abrocitinib based on the EASI-75.

Secondary Objectives:

The secondary objectives of this non-interventional study are:

- To document the efficacy of abrocitinib treatment based on physicians' assessment:
 - Physician's global assessment of AD: Scoring Atopic Dermatitis (SCORAD), EASI, IGA change to baseline.
- To document the efficacy of abrocitinib treatment based on patients' assessment:
 - Patient's global assessment of AD: change in quality of life, Dermatology Life Quality-Index (DLQI), Patient Oriented Eczema Measure (POEM);
 - Patient's assessment of anxiety and depression: Hospital Anxiety and Depression Scale (HADS);
 - Patient's assessment of pruritus: Peak Pruritus Numeric Rating Scale (PP-NRS), mean-NRS and sleep: Medical Outcomes Study Sleep (MOS) Scale;
 - Meeting the patient's expectations (change in the Patient Benefit Index [PBI]) with regard to medical treatment;
 - Number of days with topical-treatment use (topical corticosteroid (TCS)), topical calcineurin inhibitor (TCI);
 - Number of days with emollients use.

Explorative objectives:

The explorative objectives of this non-interventional study are:

- To document patient characteristics and treatment decisions in terms of:
 - Patient characteristics, clinical history, comorbidities and previous therapies;
 - Reasons for starting/ending treatment with abrocitinib, concomitant treatments;
 - Dosage and actual use of abrocitinib as assessed by the treating physician and the patient.

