9. RESEARCH METHODS

9.1. Study Design

This prospective, single-arm, multi-center, observational non-interventional study in Germany does not interfere with the current routine practice of the treating physician. All treatment decisions, types and timing of disease monitoring, diagnostic or other medicinal procedures are at the discretion of the treating physician and patients and are not influenced or affected by the participation in this non-interventional study.

All assessments described in this protocol are performed as part of normal clinical practice or standard practice guidelines for the patient population and healthcare provider specialty in the countries where this non-interventional study is being conducted. There will be no additional diagnostic or monitoring procedures that are outside the routine clinical practice.

This is a 60-month, prospective, non-interventional, multicenter study to evaluate the effectiveness, usage and patient characteristics of abrocitinib in patients with moderate to severe AD in a real-world setting.

Eligible patients will be followed up for 12 months from the date of enrollment. Patients who are switched from abrocitinib therapy to other therapies continue to be observed. Patient documentation is expected quarterly as per standard clinical practice.

Strength of this non-interventional study is the observation of drug prescription and follow-up visits in a daily medical care setting. Therapeutic strategies, patient selection and frequency of patient follow-up are decided by the treating physician.

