9.2.4.5. Treatment of Atopic Dermatitis with Abrocitinib

At the baseline visit (Visit 1) reason of starting or re-starting treatment with abrocitinib will be documented. At each visit (Visit 1-6) dose of treatment with abrocitinib and reason for its choice will be documented. If an escalation or a de-escalation of dosage occurred since the last visit, in addition stop date of previous dosage, start date of new dosage and reason for switch (lack of efficacy or intolerability) will be documented.

If treatment with abrocitinib got terminated since the last visit, reasons for ending abrocitinib treatment, stop date of treatment, start date of other new treatment and reason for switch (lack of efficacy or intolerability) will be documented.

At Visits 2-6, the investigator will ask the patient for his or her self-assessment of compliance in terms of number of abrocitinib-free days since the last visit.

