treated patient will be recorded. In order to understand not only the treatment management and reasons for starting treatment with abrocitinib, but also the reasons for ending therapy with abrocitinib, all patients will be followed up for the full individual observation period of 12 months after first abrocitinib prescription after inclusion in this observational study regardless of whether they are constantly treated with abrocitinib.

Taking into account the more diverse patient population in the real-world setting, this non-interventional study will further provide additional short-and long-term real-world evidence for the effectiveness of abrocitinib in patients of medical interest and need, who may have been underrepresented in the controlled settings of clinical trials and evaluate patient-relevant endpoints including measurements of patient-reported outcomes, such as quality of life, depression, pruritus, and sleep quality.

Patient preference and satisfaction of a therapy strongly affects adherence to a prescribed medication, ultimately affecting treatment outcome and efficacy. A factor known to have an impact on patient satisfaction with a prescribed treatment is the route of administration. Here, several studies point to a preference for oral therapies. Thus, this non-interventional study will document patient's expectations and satisfaction with regards to the treatment.

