5.3 OTHER ANALYSIS SET

The modified Full Analysis Set (mFAS) consists of all patients who met the eligibility criteria, received at least one dose of abrocitinib and had at least one post-baseline visit. This population will be used for analysis of primary and secondary endpoints, if $\geq 10\%$ of the FAS is omitted.

The Per Protocol Set (PP) consists of all patients who met the eligibility criteria, received at least one dose of abrocitinib and completed all visits, irrespective of the time-window.

This population will be used for analysis of primary and secondary endpoints, if $\geq 10\%$ of the mFAS is omitted.

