5.4 SUBGROUPS

The following subgroups will be analysed:

- Sequence of dosage (50 mg → 100 mg vs. 100 mg → 50 mg vs. 100 mg → 200 mg vs. 200 mg → 100 mg vs. 200 mg vs. 50 mg)
- Medication history* (prior conventional systemic treatment, prior biologic, prior JAKi, none of those)
- Dosage switchers (patients who switched from abrocitinib vs. patients who remain on abrocitinib)
- Abrocitinib responder, defined as: EASI-75-responder and/or SCORAD-75-responder and/or IGA 0/1
- EASI-90 responder (yes vs. no)

If less than 20 patients are in one subgroup class, classes will be combined in a meaningful way or the subgroup analysis will be omitted with reason.

*Pfizer will assign the prior medication documented to (i) topical (TCS,TCI,other), (ii) systemic (conventional, biologics, JAKi, other), (iii) phototherapy and (iv) other in order to analyze the pretreatment and form the subgroup "medication history" accordingly.

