8.2.1 Safety Analyses

Treatment-emergent adverse events are adverse events which worsen or start after start of treatment with abrocitinib but no later than 28 days after end of treatment with abrocitinib.

In addition to the analysis of treatment-emergent adverse events and drug-related adverse events as specified in 6.2 adverse events which occurred under another systemic treatment, following cessation of abrocitinib, will be given and presented in a separated listing. Number and percentage of SOC and PT will be presented according to maximal grade.

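### The SAP has no visit-level rule for effectiveness data recorded after a switch to another systemic drug, so any such data enter the rates reported as abrocitinib efficacy

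*SAP*

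**What the plan says.** Protocol section 8 sets the aim: "The primary objective of this non-interventional study is to describe the efficacy of abrocitinib treatment". Protocol 9.1 keeps switchers in the study: "Patients who are switched from abrocitinib therapy to other therapies continue to be observed". The SAP introduction fixes follow-up at 12 months "regardless of whether they are constantly treated with abrocitinib".

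The FAS (SAP 5.1) needs consent, eligibility and one dose, and "This population will be used for all analyses except safety". In SAP 5.3 the mFAS adds one post-baseline visit. The Per Protocol set takes eligible patients who "received at least one dose of abrocitinib and completed all visits, irrespective of the time-window". None of the three requires the patient to be on abrocitinib when scored.

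SAP 6.1 and 8.2.3 define the primary endpoints (IGA 0/1 and EASI-75 at Month 3) without a treatment condition. They count secondary EASI-75, EASI-90 and IGA 0/1 responses whatever the time point. 'Abrocitinib responder' (SAP 5.4 and Appendix 1) also has no treatment condition. Visits are assigned by study day only.

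For safety the SAP does separate exposures. SAP 8.2.1 ends the treatment-emergent window 28 days after abrocitinib stops, and "adverse events which occurred under another systemic treatment, following cessation of abrocitinib, will be given and presented in a separated listing". The nearest effectiveness counterpart is a subgroup in SAP 5.4: "Dosage switchers (patients who switched from abrocitinib vs. patients who remain on abrocitinib)".

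**The concern.** Suppose a patient does poorly on abrocitinib, starts another systemic drug and clears on it. Under the definitions as written, that patient is a responder at the later visit, an any-time responder, and a member of the 'Abrocitinib responder' class. The successor's response is credited to abrocitinib, while the successor's later adverse events are listed apart from it.

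The study is descriptive, so the reported percentages are its main product. If their definition does not say which drug a response belongs to, a reader cannot tell what the rate measures. Two analysts could also handle post-switch visits differently and both claim to follow the SAP. The 12-month results are more exposed than the Month 3 results, because more patients can have switched by then.

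**Working it through.** **Text check.** The plan states no switch rate, response rate or precision target, so there is no figure to reproduce. I looked in SAP 5.1–5.4, 6.1, 7, 8.2.3 and Appendix 1 for any rule that excludes, censors, recodes or separates effectiveness visits after a stop or switch. There is none apart from the patient-level subgroup. Retention of these visits therefore follows from continued observation, the one-dose FAS and the absence of a rule; the SAP does not state it in words.

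**Fixed visit.** All inputs are assumptions:
- s = share of scored patients who have already started a successor systemic drug;
- p = response rate among those still on abrocitinib;
- q = response rate among the switched.

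Formulas:
- Rate as planned: A = (1 − s)p + sq
- Switchers counted as non-responders: C = (1 − s)p
- A − C = sq, never negative
- A − p = s(q − p), which takes the sign of q − p

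Month 3, s = 5–15% and q = 30–50%: 0.05 × 0.30 = 1.5 points; 0.15 × 0.50 = 7.5 points.

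Wider grid with p = 60%:

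| s | q | A | C | A − C | A − p |
|---|---|---|---|---|---|
| 5% | 30% | 58.5% | 57.0% | +1.5 | −1.5 |
| 5% | 70% | 60.5% | 57.0% | +3.5 | +0.5 |
| 20% | 30% | 54.0% | 48.0% | +6.0 | −6.0 |
| 20% | 70% | 62.0% | 48.0% | +14.0 | +2.0 |
| 40% | 30% | 48.0% | 36.0% | +12.0 | −12.0 |
| 40% | 70% | 64.0% | 36.0% | +28.0 | +4.0 |

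One case shows both comparisons. With s = 35%, p = 60% and q = 50%, C = 0.65 × 0.60 = 39.0% and A = 39.0% + 0.35 × 0.50 = 56.5%. That is 17.5 points above C but 3.5 points below the on-abrocitinib rate of 60%.

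**Any-time response.** Let r be the share who ever respond on abrocitinib, f the share who switch without having responded, and q the share of those who respond on the successor. The planned rate is r + fq, against r on abrocitinib. A patient who responded before switching is already counted, so the excess is fq, not sq, and cannot be negative. With r = 60%, f = 10–30% and q = 50–70% (assumed):
- low: 60% + 0.10 × 0.50 = 65%
- high: 60% + 0.30 × 0.70 = 81%

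If the SAP's time-point wording instead means each visit separately, the fixed-visit formulas apply.

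**Scale.** At N = 750 and p = 60%, the 95% CI half-width is 1.96 × √(0.60 × 0.40 / 750) = 3.5 points. The low end of the Month 3 range lies inside that and the high end outside.

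**Subgroup.** The switched/remain split classifies patients, not visits. The switched class pools visits before and after the switch, and the overall FAS, mFAS and PP rates do not change. Under SAP 5.4, classes with fewer than 20 patients may be combined or the analysis omitted.

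**The case against.** **Post-switch scores may not be recorded.** In Table 1, only flares, hospitalisations, absent days and topical/emollient days are marked as collected whatever the treatment status. The EASI, IGA, SCORAD and PRO rows lack that mark. Protocol 10.3 says only that a discontinued patient may remain where follow-up can be documented. Missing values are excluded, so an unscored switcher adds nothing to the numerator. This stands: recording is likely, since these scores are scheduled at every visit with no on-treatment limit, but it is not explicit. For this reason s is defined as switched and scored.

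**The design is a treatment-policy one.** Following patients whatever they take is legitimate, and a by-visit all-observed rate is a valid summary. This also stands, and it argues against replacing that rate. But the SAP never declares the strategy, and the stated objective is abrocitinib efficacy.

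**The bias favours the drug.** A reader might infer that the plan overstates abrocitinib response at every visit. The documents do not support that. At a fixed visit the upward direction holds only against counting switchers as non-responders; against the on-abrocitinib rate it can go either way.

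**The subgroup already handles it.** The class remaining on abrocitinib does show results free of a successor drug, but it is a selected group and does not correct the any-time endpoints or the responder class.

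The table shells are a separate document that I have not seen.

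**Conclusion.** The gap is real and should be fixed, though it does not invalidate the plan. What is established from the text is that no visit-level rule exists for effectiveness after a switch, that no analysis set supplies one, and that the any-time responder endpoints and the 'Abrocitinib responder' class can credit a successor drug's response to abrocitinib. For those the effect is only upward.

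By-visit rates exceed the switcher-as-non-responder rate by s × q: 1.5 to 7.5 points at Month 3 if s = 5–15% and q = 30–50%. The primary endpoints are probably least affected, because a patient must stop abrocitinib, start a successor and respond on it by day 105. The later and larger values in the grid show what is possible and are not a forecast. Every size rests on assumed rates and on skin scores being recorded after the switch.

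**What to change.** Amend SAP 5.4, 6.1, 8.2.3 and Appendix 1 before database lock:

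1. Count any-time EASI-75, EASI-90 and IGA 0/1, and membership of the 'Abrocitinib responder' class, only from visits before another systemic AD treatment starts.
2. For every by-visit response endpoint, both primary endpoints included, keep the all-observed rate and label it 'abrocitinib and subsequent therapy'. Beside it, report a rate in which visits after the start of a successor systemic drug count as non-response. State the denominator of each, including how a switcher with no score at that visit is handled.
3. Show continuous scores before and after the switch in separate columns with n, and note that the on-abrocitinib column is a selected group.
4. Key the flag to the successor's start date, not to a permanent stop of abrocitinib. The documents allow for intermittent use and re-initiation, so a stop-based flag could misclassify temporary interruptions.
5. State whether EASI, IGA, SCORAD and the PROs are recorded after discontinuation, and align Table 1 with the answer.

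The dates needed are already collected: Protocol 9.2.4.5 asks for "stop date of treatment, start date of other new treatment and reason for switch". The cost is one derived flag per visit, some extra table columns, and somewhat lower response rates in the added analysis. No new data collection is needed.
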